12.5.2.5 Assessment of Cough

Cough questionnaire is assessed on a daily basis from Day -2 to Day 6, at Day 30 Visit, Day 60 Visit and Day 90 Visit. Questionnaire details are reported in Section 7.4.7 “Cough Assessment”.

The number and % of subjects reporting cough will be summarized over the study by study arm for the safety and PP population and by product use pattern categories for the Safety population. The responses to the individual items, including the VAS evaluating the level of cough bother and 3 Likert scales measuring the intensity, the frequency of cough and the amount of sputum production will be summarized over the study by study arm for all subjects who filled in the questionnaire and reported cough (Table 15.2.4.22.X). If a subject has answered question more than once then the most severe intensity/frequency/sputum production is presented for the “over the study” tables. No assumptions will be made in case of missing intensity/frequency/sputum production. The number and % of subjects reporting cough, The responses to the individual items, including the VAS evaluating the level of cough bother and 3 Likert scales measuring the intensity, the frequency of cough and the amount of sputum production will be listed and summarized on each day by study arm and by product use pattern categories (Table 15.2.4.23.X and Table 15.2.4.24.X) for all subjects who filled in the questionnaire and reported cough. The answers to the open question(s) related to any other important observation will be listed (Listing 15.3.4.4).

In addition, a GEE model will be used to evaluate the differences between proportions (with 2-sided p-values) and 95% CI for the need to cough between CHTP 1.2-use and CC-use at

V2, V3 and V4 in the per protocol population and in the safety population (Table 15.2.4.26.X). The model will include terms for visit, baseline level and its interaction with visit, sex, and product use pattern category and its interaction with visit. The point estimate and 95% CI of proportions and the Odds Ratios (with 2-sided p-values) will also be produced for CHTP 1.2 (CHTP 1.2 arm) versus CC (CC arm) and for CHTP 1.2 Dual-use (CHTP 1.2 arm) versus CC-use (CC arm). The interaction term will be removed if $p > 0.1$.

The SAS code to be used is shown below:

```
proc glimmix data = _data_ ;  
  class trtan avisit sex usubjid;  
  model aval = base base*visit pattern avisit sex  
  trtan*pattern/dist = binomial link=logit solution;  
  random _residual_/subject=usubjid type = un;  
  lsmeans trtan*avisit ;  
run;
```

For the confinement period, a similar model will be run, replacing the product use category with the treatment arm (Table 15.2.4.25.X).

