7.7.2.2 Assessment of Cough-VAS

Subjects will be asked to self-report and to assess the respiratory symptom "cough" on a VAS, on three Likert scales, and with an open question. Assessment of cough reflecting the cough symptoms in the last 24 hours will be conducted irrespective of the time of product use.

Subjects will be asked if they have experienced a regular need to cough, e.g., whether they have coughed several times in the previous 24 hours prior to assessment. If the answer is "yes", subjects will be asked to complete a VAS, 3 Likert scale questions and the open question.

On the VAS, subjects will assess how bothersome their cough was during the previous 24 hours. The VAS ranges from "not bothering me at all" to "extremely bothersome".

Furthermore, subjects will assess the intensity and frequency of cough and the amount of sputum production during the previous 24 hours on Likert scales.

The intensity of cough will be assessed on a 5-point Likert scale ranging from 1 to 5, with 1 = very mild – 2 = mild – 3 = moderate – 4 = severe – 5 = very severe.

Confidentiality Statement

Data and information contained in this document are considered to constitute trade secrets and confidential commercial information, and the legal protections provided to such trade secrets and confidential information are hereby claimed under the provisions of applicable law. No part of this document may be publicly disclosed without the written consent of Philip Morris Products S.A.

The frequency of cough will be assessed on a 5-point Likert scale ranging from 1 to 5, with 1 = rarely – 2 = sometimes – 3 = fairly often – 4 = often – 5 = almost always.

The amount of sputum production will be assessed on a 4-point Likert scale ranging from 0 to 3, with 0 = no sputum – 1 = a moderate amount of sputum – 2 = a larger amount of sputum – 3 = a very large amount of sputum.

Finally, subjects will be asked to share any other important observations with the site collaborators about their coughing.

See [Appendix A](#) for the time points of assessment.

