9.2.3 Exposure Period (Days 1 to 5)

[Table 9](#) shows the assessments that will be performed on Day 1.

The collection of 24-hour urine of Day 1 starting on Day 1 will end on Day 2.

Table 9 Time Schedule – Day 1

Time	Blood Sample	Procedures	Additional Information
		Day 1	
		Allocation to study arm	
6:30 AM		Start of use of IPs	
Prior to 11:30 AM		AE/SAE recording	
Prior to 11:30 AM		Concomitant medications	
Prior to 11:30 AM		End of 24-hour urine sample collection for Day -1	The urine is collected for 24 hours \pm 1 hour. The end of the 24-hour urine collection should be prior to first use of IPs.
Prior to 11:30 AM		Start of 24-hour urine sample collection for Day 1.	The start of 24-hour urine collection of Day 1 should be subsequent to the end of 24-hour urine collection of Day -1
Prior to 11:30 AM		Urine sample to be taken from the 24-hour urine of Day -1	Aliquots from 24-hour urine will be collected according to Table A2 . Bio-banking for biomarkers (if additional consent is obtained)
Prior to 11:30 AM		Vital signs (blood pressure, pulse rate, respiratory rate)	At least 5 minutes in supine position, at least 15 minutes after having stopped using IP
Prior to 11:30 AM		Assessment of cough (VAS)	Has to be done prior to allocated IPs

Confidentiality Statement

Data and information contained in this document are considered to constitute trade secrets and confidential commercial information, and the legal protections provided to such trade secrets and confidential information are hereby claimed under the provisions of applicable law. No part of this document may be publicly disclosed without the written consent of Philip Morris Products S.A.

Time	Blood Sample	Procedures	Additional Information
Start of Procedure		Day 1	
In the evening prior to 9:30 PM (approx. 8:00 PM ± 1.5 hour)		CO breath test	
In the evening prior to 9:30 PM (approx. 8:00 PM ± 1.5 hour)	√	COHb in blood	
In the evening prior to 9:30 PM (approx. 8:00 PM ± 1.5 hour)	√	Plasma nicotine and cotinine sample	Cotinine will be measured in the same assay as nicotine. No additional blood samples required
8:00 PM - 11:00 PM		QSU brief Questionnaire	
8:00 PM - 11:00 PM		MCEQ Questionnaire	
11:00 PM		End of use of IPs	
6:30 AM - 11:15 PM		Collection of used CC butts	For accountability
6:30 AM - 11:15 PM		Collection of used CHTP 1.2	For accountability

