PP	Per protocol
PT	Preferred Term
PX	Paraxanthine
QC	Quality control
QSU-brief	Questionnaire of Smoking Urges
QTcB	QT Interval Corrected using Bazett's Formula

QTcF	QT Interval Corrected using Fridericia's Formula
RRP	Reduced risk products
SA	Smoking Abstinence
SAP	Statistical Analysis Plan
S-BMA	S-benzylmercapturic acid
SD	Standard deviation
SDTM	Standard Data Tabulation Modul
SES	Socio-Economic Status
sICAM-1	Soluble inter-cellular adhesion molecule-1
SOC	System Organ Class
SOP	Standard Operating Procedure
S-PMA	S-phenylmercapturic acid
T	Time point
TAC	Total anti-oxidant capacity
TC	Total cholesterol
TFL	Tables, Figures, and Listings
TG	Triglycerides
Total 1-OHP	Total 1-hydroxypyrene
Total 3-OH-B[a]P	Total 3-hydroxybenzo(a)pyrene
ULOQ	Upper Limit of Quantification
VAS	Visual Analogue Scale
WBC	White blood cell (count)
WHO	World Health Organisation
YG1024+S9	Ames Mutagenicity Test

The following special terms are used in this SAP:

Admission period	Day -3 until start of baseline period.
Baseline period	06:30 AM at Day -2 until 06:29 AM of Day 1.
Carbon Heated Tobacco Product 1.2 (CHTP 1.2)	CHTP 1.2 is a non-menthol tobacco stick which is comparable in shape and form, and is used in a similar manner to a combustible cigarette except that the tobacco contained in the CHTP 1.2 is heated by a Carbon Heat Tip and not burned like in a combustible cigarette.
Combustible cigarette (CC)	The term 'combustible cigarette' refers to commercially available cigarettes (manufactured) and excludes cigars, pipes, bidis, and other nicotine-containing products.
Completer	A subject is considered to have completed Confinement, period 2, 3 and 4 if he/she did not discontinue before Day 6, Day 30 Visit, Day 60 Visit, and Day 90 Visit respectively, and Completed safety follow-up.
Day of Discharge in the Confinement setting	Day 6 or early discontinuation in confinement.
Day of Discharge in the Ambulatory setting	Second day of Day 90 Visit.
Enrolment	On Day -3 for eligible subjects after all applicable inclusion and exclusion criteria have been satisfactorily met.
Enrolled	A subject is considered as being enrolled once he/she is declared for being enrolled in the IxRS.
Exposure period	In the confinement setting: 06:30 AM of Day 1 until the time of discharge on Day 6. In the Ambulatory Setting: from Discharge on Day 6 until Discharge at Day 90 Visit.

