**Figure 1 Study Flowchart**

- The Screening Period (from Day -45 until Admission on Day -3):

The Screening Period covers 6 weeks prior to Admission to the site. A demonstration of CHTP 1.2 (without product use) will be done by the site staff during the Screening Visit (Visit 1). At the Screening Visit, spirometry needs to be done at least 1 hour after having stopped smoking.

- The Admission Day (from Admission on Day -3 until 06:29 AM of Day -2):
Subjects will be in a confinement setting for 9 days from Day -3 onwards.

On Day -3 (Admission), after all inclusion/exclusion criteria are checked, all eligible subjects will be enrolled and perform a product test using up to 5 CHTPs 1.2. However, before smoking and the product testing, the sample for CYP2A6 activity has to be taken. After the product test, subjects not willing and ready to use the CHTP 1.2 will be discontinued. After the sample for CYP2A6 activity has been taken, and the product test has been performed, smokers will be allowed to smoke their single preferred brand of CC *ad libitum* until 11.00 PM. Use of any tobacco/nicotine containing product other than CC and CHTP 1.2 for the product test will not be allowed after Admission.

- The Baseline Period (from Day -2, 06:30 AM until Day 1, 06:29 AM):

All subjects will continue smoking their CC *ad libitum*. Twenty four-hour urine collection for Day -2 will start in the morning of Day -2 ending in the morning of Day -1. Twenty four-hour urine collection for Day -1 will start in the morning of Day -1 ending in the morning of the Day 1. On Day -2 and Day -1, smoking will be allowed from 06:30 AM until around 11:00 PM. However, on Day -2, smoking will be allowed only after the Cough Questionnaire has been completed.

On Day -1, subjects will be randomized to 1 of the 2 study arms in a 2:1 ratio using a stratified randomization.

- CHTP 1.2 arm: ~80 subjects, *ad libitum* use of CHTP 1.2
- CC arm: ~40 subjects, *ad libitum* use of their own preferred CC brand

Subjects will be informed about their randomized study arm by the study site staff on Day 1 prior to 06:30 AM.

- The Exposure Period (from Day 1, 06:30 AM until Discharge at Day 90 Visit):

The exposure period will include both the exposure period in confinement, and the exposure period in the ambulatory setting:

- The Exposure Period in the Confinement Setting (from Day 1, 06:30 AM until the time of Discharge on Day 6):

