7.4.7 Cough Assessment

Subjects will be asked to self-report and to assess the respiratory symptom “cough” on a VAS, on three Likert scales, and with an open question. Assessment of cough reflecting the cough symptoms in the last 24 hours will be conducted irrespective of the time of product use.

Subjects will be asked if they have experienced a regular need to cough, e.g., whether they have coughed several times in the previous 24 hours prior to assessment. If the answer is “yes”, subjects will be asked to complete a VAS, 3 Likert scale questions and the open question.

On the VAS, subjects will assess how bothersome their cough was during the previous 24 hours. The VAS ranges from “not bothering me at all” to “extremely bothersome”.

Furthermore, subjects will assess the intensity and frequency of cough and the amount of sputum production during the previous 24 hours on Likert scales as presented in **Table 6**.

Table 6 Cough Assessment Likert Scales

Question	Likert Scale
1 The intensity of cough	1 = very mild 2 = mild 3 = moderate 4 = severe 5 = very severe
2 The frequency of cough	1 = rarely 2 = sometimes 3 = fairly often 4 = often 5 = almost always
3 The amount of sputum production	0 = no sputum 1 = a moderate amount of sputum; 2 = a larger amount of sputum; 3 = a very large amount of sputum.

Finally, subjects will be asked to share any other important observations with the site collaborators about their coughing.

Cough Assessment will be done daily from Day -2 to Day 6 prior product use but no later than 11:30 AM. It will also be done at Day 30 Visit, Day 60 Visit, and Day 90 Visit (second day of the respective visits) no later than 11:30 AM, irrespective of product use.

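### The over-study cough tables are not limited to exposure, so they can count cough from before the assigned product; severity is tabulated among coughers only

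*SAP*

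**What the plan says.** **Schedule.** SAP 12.5.2.5 states: "Cough questionnaire is assessed on a daily basis from Day -2 to Day 6". It adds the Day 30, 60 and 90 Visits. SAP 7.4.7 fixes the time of day: "Cough Assessment will be done daily from Day -2 to Day 6 prior product use but no later than 11:30 AM". The recall period is one day (Protocol 7.7.2.2: "Assessment of cough reflecting the cough symptoms in the last 24 hours").

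**Start of exposure.** SAP section 4 defines the exposure period: "In the confinement setting: 06:30 AM of Day 1 until the time of discharge on Day 6". For the Day 1 cough assessment, the Protocol 9.2.3 schedule says: "Has to be done prior to allocated IPs".

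**Over-study tables.** SAP 12.5.2.5 tabulates by arm the number and percentage of subjects reporting cough, and the item responses, over the study (Tables 15.2.4.22.1 and 15.2.4.22.2). The rule for repeats is: "If a subject has answered question more than once then the most severe intensity/frequency/sputum production is presented". It names intensity, frequency and sputum. It does not name the VAS, and it is confined to the over-study tables.

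**Denominator for severity.** The VAS and Likert items are summarized "for all subjects who filled in the questionnaire and reported cough". This holds for the over-study and the daily summaries. It follows from the questionnaire, which puts these items only to subjects who first report a regular need to cough.

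**Also planned.** There are tables by arm and study day (15.2.4.24.x), ambulatory tables by product use period (15.2.4.23.x), and models of the yes/no cough item in confinement (15.2.4.25.x) and at the ambulatory visits (15.2.4.26.x).

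**The concern.** Two features are at issue.

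First, if a table records whether a subject ever coughed, or the worst answer given, and its window opens before the assigned product is used, a subject who coughed at baseline and then stopped looks the same as one who never stopped. Both arms carry the same pre-exposure cough, so the arms are drawn together whichever way the product acts.

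Second, a subject who no longer reports cough drops out of the severity summary. The arms are then compared on subsets formed after randomization, and a product that removes mild coughs leaves a subset with a higher average severity.

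Cough is both a secondary endpoint (under the lung-function objective) and a safety variable, so readers may take the over-study table as the summary result.

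**Working it through.** The documents give no cough rate, severity, sample size or power for cough, so there is no figure to reproduce. Only the assessment count comes from the documents; every rate below is an assumption.

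**Step 1: count.** Days -2, -1 and 1 to 6 make 8 assessments, and three visits make 11. Day -2 looks back on Day -3, Day -1 on Day -2, and Day 1 on Day -1. So 3 of 11 (27%) precede the assigned product and 8 follow it. On the endpoint window in SAP 5.2, objective 5 (Day 1 to Day 90 Visit), Days -2 and -1 fall out, leaving 9 assessments of which Day 1 is still pre-product.

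**Step 2: dilution of the proportion ever coughing.** Let p0 be the daily probability of cough on cigarettes and p1 that on CHTP 1.2, with k pre-product and 8 post-product assessments. With independent days:

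- CC arm: 1 - (1 - p0)^(k+8)
- CHTP 1.2 arm: 1 - (1 - p0)^k × (1 - p1)^8

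Example with p0 = 0.30, p1 = 0.15, k = 3: CC 1 - 0.7^11 = 0.980; CHTP 1.2 1 - 0.7^3 × 0.85^8 = 0.907; ratio 0.92. With k = 1: 1 - 0.7^9 = 0.960 and 1 - 0.7 × 0.85^8 = 0.809; ratio 0.84. With k = 0: 0.942 and 0.728; ratio 0.77.

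| Assumed p0 to p1 | Ratio, 11 assessments | Ratio, 9 (from Day 1) | Ratio, 8 (from Day 2) |
|---|---|---|---|
| 0.20 to 0.10 | 0.85 | 0.76 | 0.68 |
| 0.30 to 0.15 | 0.92 | 0.84 | 0.77 |
| 0.40 to 0.20 | 0.97 | 0.91 | 0.85 |
| Halved, fully persistent cough | 1.00 | 1.00 | 0.50 |

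The last row assumes that each subject coughs at all or none of the assessments in a phase, and that later coughers are baseline coughers. One pre-product assessment is then enough to hide the effect. With independent days some attenuation remains after the window is cut to 8, because counting any cough over many days saturates; that part is not due to the pre-product assessments.

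**Step 3: dilution of the worst intensity.** A simulation (200,000 subjects per scenario, latent normal severity, within-subject correlation 0.8, 31% coughing per day, intensity 1 to 5 asked of coughers) applied a 1 SD improvement on CHTP 1.2. Mean worst intensity among coughers, CC against CHTP 1.2:

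- 11 assessments: 2.52 against 2.29, a gap of 0.23
- 8 post-product assessments: 2.46 against 1.81, a gap of 0.65

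**Step 4: the coughers-only denominator.** Take 80 subjects, 16 with mild cough, 16 with severe cough and 48 not reporting cough. Suppose the mild coughs resolve.

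- Severe among coughers: 16/32 = 50% becomes 16/16 = 100%.
- Severe among all respondents: 16/80 = 20% before and after.
- Not reporting regular cough: 48/80 = 60% becomes 64/80 = 80%.

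The first line looks like deterioration; the other two show what happened. In the simulation, with 80% of milder coughs stopping, single-day mean intensity among coughers was 2.11 (CC) against 2.99 (CHTP 1.2), with 31% against 14% coughing. Cutting the over-study window to 8 assessments does not cure this: 2.46 against 2.92. With a uniform 1 SD shift there was no reversal (single day: 2.11 against 1.66).

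**The case against.** The strongest reply is that inclusion of Days -2 and -1 is read from silence. SAP 5.2 sets the cough endpoint at Day 1 to the Day 90 Visit, under an objective about the exposure period, and table detail is left to a separate shells document that is not available here. That stands: a reader might infer that the SAP expressly counts all three pre-product assessments, and it does not. It is only the plain reading of 12.5.2.5. But the endpoint window still admits the Day 1 assessment, and Step 2 shows that one can be enough.

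A second reply is that other outputs already carry the result. Largely so. The daily tables and yes/no models are free of the window problem, and those models keep non-coughers in. A reader might infer that all cough output is compromised; the worst-answer rule reaches only Tables 15.2.4.22.x. These safeguards do not extend to severity: no model analyzes it, and the daily severity tables use the same coughers-only denominator. The ambulatory model also compares product use categories rather than randomized arms.

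Third, Day -2 is not purely a cigarette assessment. Its recall covers Day -3, when "all eligible subjects will be enrolled and perform a product test using up to 5 CHTPs 1.2". That is correct, and for the Safety Population, defined by any CHTP 1.2 exposure, Day -2 follows first use of the product. The test preceded randomization and was common to both arms, so the dilution argument is unchanged, but Day -2 should not be labelled a clean baseline.

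Fourth, it is tempting to score non-coughers as VAS 0 and no sputum. The objection to this is sound. The first question asks about a regular need to cough, so a no does not establish zero bother or absence of sputum.

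**Conclusion.** The point holds for Tables 15.2.4.22.1 and 15.2.4.22.2. As written they take in up to three assessments made before the assigned product, and at least Day 1 on the narrower window, which dilutes any arm difference shown there. On the assumed rates, a true halving of daily cough appears as a relative cut of 3% to 15% in the proportion ever coughing over 11 assessments with independent days, and as none with fully persistent cough. Limiting the window to post-product assessments gives 15% to 32% and 50% respectively.

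The coughers-only severity summary is a separate and weaker point. A reader might infer that it will reverse the product effect. The working supports only that it could mislead if mild coughs resolve selectively; a uniform improvement did not reverse it, and the percentage coughing shown alongside lets a reader see the subset shrink.

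How repeated VAS answers are combined over the study is unspecified. All of this concerns descriptive tables for a secondary and safety endpoint. The primary analysis is unaffected.

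**What to change.** In SAP 12.5.2.5:

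1. Define the window for Tables 15.2.4.22.x as assessments after first use of the assigned product, Day 2 to Visit 4.
2. Show Days -2, -1 and 1 separately as pre-exposure, with a note that Day -2 recall includes the product test. Keep Day 1 as baseline in line with SAP 12.1.4 (last valid assessment before exposure-period product use).
3. State how repeated VAS answers are combined over the study.
4. In the Likert severity tables, over-study and daily, add a category for subjects who did not report regular cough, with all questionnaire respondents as denominator. Do not impute VAS 0 or no sputum. Keep the coughers-only summary alongside.

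The cost is SAP wording and table programming. No new data are needed, since the first cough question already supplies the added category.

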 - CEMA
 - HEMA
 - 3-hydroxybenzo(a)pyrene

- HMPMA
4. To describe the levels of nicotine over the entire exposure period in smokers switching from CC to CHTP 1.2 as compared to smokers continuing to use CC.
- Endpoints (Day 1 to Day 90 Visit):
- Nicotine equivalents (NEQ = molar sum of free nicotine, nicotine-glucuronide, free cotinine, cotinine-glucuronide, free trans-3'-hydroxycotinine, trans-3'-hydroxycotinine-glucuronide), expressed as concentration adjusted for creatinine in 24-hour urine
 - Nicotine and cotinine plasma concentrations
5. To determine the changes over the entire exposure period in lung functions in smokers switching from CC to the CHTP 1.2 as compared to those continuing to use CC
- Endpoint (Day 6 and Day 90 Visit):
- Spirometry (pre- and post-bronchodilator):
 - forced expiratory volume in 1 second (FEV₁),
 - forced vital capacity (FVC),
 - FEV₁/FVC,
 - forced expiratory flow (FEF 25-75)
- Endpoint (Day 1 to Day 90 Visit):
- Cough assessment by Visual Analog Scale (VAS) and Likert Scales and one open question.
6. To monitor selected cardiovascular clinical risk endpoints over the entire exposure period in smokers switching from CC to CHTP 1.2 as compared to smokers continuing to use CC
- Endpoints (Day 6 to Day 90 Visit):
- Systolic and diastolic blood pressure on Day 6, at Day 30 Visit, Day 60 Visit, and Day 90 Visit
 - High sensitive C-reactive protein (hs-CRP), blood glucose, myeloperoxidase (MPO), low density lipoprotein (LDL), high density lipoprotein (HDL), triglycerides (TG), and total cholesterol (TC) in serum at Day 30 Visit, Day 60 Visit, and Day 90 Visit.
 - Fibrinogen, homocysteine in plasma at Day 30 Visit, Day 60 Visit, and Day 90 Visit.
 - Hemoglobin A1c (HbA1c) in blood at Day 90 Visit.
 - Apolipoprotein A1 (Apo A1) and apolipoprotein B (Apo B) in serum at Day 90 Visit.
 - Soluble inter-cellular adhesion molecule-1 (sICAM-1) in serum on Day 6, at Day 30 Visit, Day 60 Visit, and Day 90 Visit.
 - White blood cell (WBC) and platelet counts in blood on Day 6, at Day 30 Visit, Day 60 Visit, and Day 90 Visit.

- 11-dehydro-thromboxane B2 (11-DTX-B2) in 24-hour urine on Day 5, at Day 30 Visit, Day 60 Visit, and Day 90 Visit (expressed as concentration adjusted for creatinine).
 - Body weight and waist circumference at Day 90 Visit.

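### For Visits 2 to 4 the SAP text specifies no model-based comparison of cough by randomized arm: its tests set product-use groups against the CC arm, and the printed SAS code does not match the stated model

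*SAP*

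**What the plan says.** Objective 5 in SAP section 5.2 reads "To determine the changes over the entire exposure period in lung functions in smokers switching from CC to the CHTP 1.2", with smokers who stay on CC as the comparison. One of its endpoints, running from Day 1 to the Day 90 Visit, is "Cough assessment by Visual Analog Scale (VAS) and Likert Scales and one open question".

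SAP section 12.5.2.5 plans three things for cough:

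- **Descriptive summaries** by arm, over the study and on each assessment day, in the safety and per-protocol (PP) populations (Tables 15.2.4.22.x and 15.2.4.24.x).
- **An ambulatory GEE** (reported in Table 15.2.4.26.x) for the need to cough at Visits 2, 3 and 4, in the PP and safety populations, specified thus: "The model will include terms for visit, baseline level and its interaction with visit, sex, and product use pattern category and its interaction with visit". Odds ratios with two-sided p-values are named for two contrasts: the CHTP-use group of the CHTP 1.2 arm against the CC arm, and the Dual-use group of the CHTP 1.2 arm against the CC arm.
- **A confinement GEE**: "For the confinement period, a similar model will be run, replacing the product use category with the treatment arm".

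The product-use categories (SAP section 6.3.3.1 and Table 7) are shares of CHTP 1.2 in all CHTP 1.2 and CC used: 70–100% (CHTP 1.2), between 30 and 70% (Dual) and 0–30% (CC). They are defined for the CHTP 1.2 arm. The PP populations are the primary set for cough (Protocol section 12.3, SAP section 10).

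**The concern.** Product-use category is observed after randomization and exists in one arm only. A test of a category against the CC arm compares part of one randomized group with all of the other. Subjects in the CHTP 1.2 arm who mostly go back to CC enter neither named contrast. If cough, or something related to cough, affects who stays on CHTP 1.2, the contrast can differ from no effect without any product effect.

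The listed terms also leave out the cigarette-consumption stratum, which was a randomization factor. The spirometry model in SAP section 12.5.2.4, under the same objective, compares the arms directly and includes that stratum. So do the models for CYP1A2, QSU-brief, mCEQ and FTND.

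At stake is whether the only ambulatory p-values for cough, which is both a secondary endpoint and a safety variable, carry the protection of randomization.

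**Working it through.** The documents state no power, rate or sample size for cough, so there is no plan figure to reproduce. The check has four parts.

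**1. What is compared, by period (SAP section 12.5.2.5).**

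- Confinement: arm is in the model.
- Visits 2 to 4, model: use category, no arm term; contrasts are use group against CC arm.
- Visits 2 to 4, by arm: descriptive tables only.

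The text therefore contains no model-based ambulatory estimate of all randomized CHTP 1.2 subjects against CC.

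**2. How far this matters in the PP set.** SAP Table 12 makes a CHTP 1.2 subject non-compliant when CC use averages more than 0.5 per day from Day 1 to the end of the period. To be Dual, CC must exceed 30% of total use.

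- If both rules use the same window: total use must be below 0.5 / 0.30 = 1.67 products per day.
- The windows need not coincide. SAP section 6.3.3.1 computes the share over each time period of interest. If all permitted CC fell in a 30-day Period 4: 0.5 × 90 = 45 CC, and 45 / 30 = 1.5 CC per day. Dual then needs total use below 1.5 / 0.30 = 5 products per day.
- Subjects entered smoking at least 10 per day. At 10 products per day, 0.5 CC gives a CHTP share of 95% and 1.5 CC gives 85%; both lie in the CHTP-use category.

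So in the PP set the CHTP-use group is practically the whole PP CHTP 1.2 arm, and the Dual group should be nearly empty on either window.

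**3. What selection could do outside the PP set (illustration; the inputs are assumed).** Let p be the cough prevalence in both arms (no product effect), s = 0.5 the share of the CHTP 1.2 arm in the CHTP-use group, and ψ the odds ratio between coughing and staying in that group. The documents give neither p nor ψ. They support s only loosely: SAP section 8 assumes that at least 50% remain in the ambulatory PP set.

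With a = P(stay | cough) and b = P(stay | no cough), solve p·a + (1 − p)·b = s and a/(1 − a) = ψ·b/(1 − b). Cough prevalence among stayers is p·a/s.

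Example with p = 0.30 and ψ = 0.5: a = 0.38, b = 0.55, prevalence among stayers 0.30 × 0.38 / 0.5 = 0.228. The apparent odds ratio is (0.228/0.772) / (0.30/0.70) = 0.69. A two-proportion test of 40 (0.5 × 80) against 40, at nominal two-sided 5%, rejects in 11.2% of trials.

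| p | ψ | Apparent odds ratio | Rejection, use group 40 v 40 |
|---|---|---|---|
| 0.2 | 0.67 | 0.81 | 6.5% |
| 0.2 | 0.33 | 0.52 | 17.6% |
| 0.4 | 0.67 | 0.82 | 7.2% |
| 0.4 | 0.33 | 0.56 | 23.0% |
| any of these | 1 | 1.00 | 5% |

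The comparison of all randomized subjects (80 v 40) rejects in 5% throughout.

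**4. Text against printed code (SAP section 12.5.2.5).**

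- The text has category-by-visit; the code has `trtan*pattern` and no category-by-visit term.
- `pattern` is a categorical variable but is missing from the CLASS statement.
- The code uses both `visit` (in `base*visit`) and `avisit`.
- `lsmeans trtan*avisit` asks for an effect that is not in the MODEL statement, and has no DIFF option, so it returns no contrast.

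The code mentions arm, but it yields neither the arm comparison nor the two named contrasts.

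**The case against.** Several points on the other side stand.

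- **By-arm results are planned.** A reader might infer that the comparison in objective 5 is missing altogether. It is not: cough is tabulated by arm on each assessment day. The objective asks for a comparison and names no test, and Protocol section 12.5.3 promises only descriptive summaries for secondary endpoints. What is missing is the model-based arm estimate. The SAP nevertheless chose to report ambulatory p-values, and those rest on use groups.
- **In the primary set the issue largely disappears.** Within PP, the CHTP-use contrast is close to the PP arm contrast used for spirometry and the biomarkers. Selection on adherence remains there, but that is a study-wide protocol choice and not a fault of the cough model.
- **The bias is conjectural.** Nothing in the documents links cough to a return to CC. With no such link there is no inflation.

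A reader might also conclude that the Dual contrast in PP is empty by construction. That goes too far. The compliance average runs from Day 1, while the use share may be taken over one period, so Dual membership is possible at low total use. Nearly empty is what the documents support.

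**Conclusion.** For Visits 2 to 4 the SAP text gives no model-based comparison of cough by randomized arm. Its odds ratios and p-values compare post-randomization use groups in the CHTP 1.2 arm with the whole CC arm, and the model omits the cigarette-consumption stratum. The practical weight lies in the safety-population run and in the lack of any test of all randomized subjects.

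The reach is limited: cough is one of many secondary endpoints, SAP section 12.1.8 makes no multiplicity adjustment for these, and no primary conclusion is touched. The documents do not support a claim that the planned estimate is biased, or biased in favour of CHTP 1.2. The odds ratios of 0.52–0.82 and rejection rates of 6.5–23% show what selection could do under the assumed prevalence, retention and association, and no more.

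The mismatch between text and code rests on no assumption and needs correction in any case.

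**What to change.** 1. Add a GEE for Visits 2 to 4 with arm, visit, arm-by-visit, baseline, sex and cigarette-consumption stratum. Run it in the PP and safety populations already planned, by randomized arm. Restrict the safety run to randomized subjects, since that population also holds people exposed only at the product test. Add a full analysis set run as sensitivity.
2. Report its arm contrasts, by visit, as the ambulatory arm comparison for objective 5.
3. Keep the product-use model as supportive and label it as a comparison of groups formed after randomization.
4. Correct the SAS code for the product-use model: category in CLASS, category-by-visit in MODEL, one name for visit, and LS means with differences for effects that the model contains. State how CC-arm subjects are coded on the category variable.

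The PP populations should stay the primary set for cough. Making the full analysis set the main one, or dropping the PP run, would override Protocol section 12.3 and is not needed to close this gap.

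The cost is one extra model run and one table. No new data are required.
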